
A.2. Clinical Trial Design Details

We will utilize the MOST procedure to assess the app suite specialty features’ efficacy and other performance aspects. MOST is explicitly designed to disentangle the effects of multiple components that make up an intervention^{26,105}—a key project goal given our intent to appraise the merit of novel, previously untested app features. Traditionally, multi-component interventions are subjected to efficacy pilot tests followed by large RCTs, but in the absence of systematic evaluations of singular components. However, in such cases: (a) the intervention may contain inert ingredients that contribute to subpar or cost-inefficient results; or (b) difficulties may arise in determining which intervention aspects contribute to efficacy, due to the presence of multiple components which have not been individually tested. In contrast, following

[figure not shown]

Figure 2. Theoretical Framework for the PA-tracking App Suite. SCT=Social Cognitive Theory; SET=Stereotype Embodiment Theory; PA=Physical activity; SA=Sedentary Activity

systematic optimization as facilitated by MOST, subsequent RCTs are expected to produce sharper, more interpretable results.

Based on recommendations from the MOST literature, we will employ a 2x2x2 factorial experiment in which three between-subject factors, corresponding to the presence vs. absence of each specialty feature, will be manipulated in a completely crossed design, given each participant's utilization of the core app. Following random assignment (using a computer algorithm designed for this purpose) to the eight conditions, participants will undergo a four-month intervention interval. Experimental outcomes will consist of pre-to-post change scores on PA-related and mediating variables, and documentation will also be provided for parameters such as usage frequency and user satisfaction that are pertinent to subsequent efforts to achieve optimization.

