Each specialty feature will be provided to half of the participants, leading to respective comparative assessments that involve 45 vs. 45 (feature present vs. absent) participants. Accordingly, it is incorrect to conceptualize this design as a test of outcome differences between eight separate inadequately powered cells; rather, the intent is to collapse information across cells so as to obtain a reasonably large sample size when examining each component's performance.[24] Further, because the specialty features would be inexpensive to download if used in large-scale distributions of the app, and because they have been carefully designed to reflect empirically supported theory, it is important to avoid premature elimination of features on the basis of non-significant experimental effects which in actuality may stem from sample size limitations. Consequently, in evaluating intervention components we will downplay the importance of (though still include) significance testing of PA outcomes, and instead will incorporate the total array of relevant information (e.g., effect sizes, usage rates, satisfaction ratings) in the final component selection and fine-tuning process.

B. Participants, Recruitment, and Consent

For Aim 1, a convenience sample of 15 elders will be recruited from independent-living communities within FPCIW's 2,000-member senior network in Los Angeles (LA) and local senior venues. An estimated 1,300 FPCIW members use smartphones.[45] Iterative phases of product development require only five to seven representative users per prototype iteration,[46] justifying our sample size of 15 (five per app suite specialty feature).

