One-hundred community-living older adults who are served by Front Porch Center for Innovation and Wellbeing (FPCIW) will be primarily recruited from FPCIW's 2000-member senior network in Los Angeles. FPCIW will facilitate recruitment, referring its eligible members to the study team. Justification for the targeted sample size is multifold. First, an adequate number of participants will be available to enable meaningful analyses (final N=90) given a four-month attrition rate of 10% (estimate based on averaging interval-adjusted study completion rates in five studies of mHealth or web-based PA interventions for adults aged >40 years[47-52]. Second, the expected overall (N=90) and per-feature (n=45) sample sizes well exceed the number of participants previously described as necessary to determine if a larger trial is warranted.[53] Third, the stipulated sample size is easily achievable and represents roughly the maximum number of participants attainable given available funding resources.

Persons will be deemed eligible based on the following criteria. Inclusion criteria: men or women, 65–84 years old; English speaking; reside in LA or in Pacific Time Zone if participating remotely; score ≥ 5 on a 6-item cognitive screener[54]; report <150 minutes of moderate-to-vigorous PA/week as per a single-item screener;[55] ambulatory; ability to safely participate in PA as determined by self-report of ability to regularly walk safely; smartphone owner for ≥ 1 month; observed ability to reliably access and operate a smartphone during orientation; available by telephone for the duration of either study. Exclusion criteria: unwillingness to meet at local community venues and/or via online meetings to comply with study procedures for the length of each study. Although not an eligibility criterion per se, access to a computer and webcam, and sufficient computer skills to participate in virtual orientation is necessary if in-person orientation is not feasible.

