|----------------------------------------------------------|-----------------------------------------------------------------------------------------------------------------------------------------------------------------------------------------------------------------------------------------------------------------------------------------------------------------------------------------------------------------|-----------------------------------------|---------------------------------------------------------------------------------------------------|----------------------------|
| Background: Demographics/ Health/ Smartphone Information | Age, Sex, Race/Ethnicity, Education, Marital Status, Living Status, Income, Employment, Health Conditions, Health Tracking Behavior, Mins PA/wk, Major Health Problems (e.g., diabetes), Smartphone Ownership Duration, Smartphone Platform, Smartphone Proficiency (self-rate 1-10), Smartphone Carrying Location, Research and Wellness Program Participation | Sample Description Potential Covariates | Demographic/Background Questionnaire [-18 items] | Baseline |
| Mediators | Views of Aging | Tests of Mediation | Attitudes to Ageing Questionnaire [24 items] | Baseline and post |
| | Aging Self-Perceptions | Tests of Mediation | Attitudes Toward Own Aging subscale of the Philadelphia Geriatrics Center Morale Scale; [5 items] | Baseline and post |
| | PA Self-Regulation, PA Self-Efficacy, PA Outcome Expectation, PA Social Support | Tests of Mediation | Health Beliefs Survey [78 items] | Baseline and post |
| PA-Related Outcomes | Objective PA Level | Primary Dependent Variable | activPAL | Baseline and post |
| | Self-Reported PA Level | Dependent Variable | Physical Activity Scale [PASE; 10 items] | Baseline and post |
| | Functional Mobility | Dependent Variable | 4-meter Walk Test | Baseline and post |
| | Objective Sedentary Time | Dependent Variable | activPAL | Baseline and post |
| Usability | Satisfaction | App Refinement | Mobile App Rating Scale – Adapted User Version [uMARS; 5 items] Interview | Post 4-month phone call |
| | Objective Usage: Proportion of days opening the app | App Refinement | App-Stored Usage Data | full study duration |

III. Data Management, Analysis, & Statistical Considerations

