Specialty feature condition effects on the *objective physical activity* (change in daily steps) primary outcome will be analyzed using a mixed effects linear regression model adjusted for confounders (including presence/absence of other specialty features, between-feature interactions, select demographic variables [age, sex, race/ethnicity, education]), and baseline daily steps. Although significance testing will provide merely one source of information in driving app optimization decisions, the anticipated sample size (N=90) was chosen to enable 80% power (given $\alpha=.10$ and a one-tailed test, as consistent with recommendations for pilot studies employing MOST) in testing experimentally based pre-post physical activity increases associated with a specialty feature (given an effect size of .45, a feasible value based on prior tests of technology-based physical activity intervention components). Using change-from-baseline scores for *objective physical activity*, we will derive Cohen's *d* effect sizes stratified by presence vs. absence of each specialty feature. For secondary physical activity-related outcomes and proposed mediators, we will conduct multiple one-tailed t-tests ($\alpha=.10$) to further explore the potential viability of the specialty features. To facilitate later RCT planning, we will also calculate single group pre-post change effect sizes for the full sample. Correlation coefficients will be calculated to assess associations between the primary outcome (change in daily steps) and proposed mediators. To analyze *app usage behavior* and *user satisfaction*, for each intervention feature considered separately, we will perform one-tailed t-tests to examine mean differences in each variable based on whether or not the participant was assigned to receive that feature.

After participants conclude the clinical trial phase, they will take part in an interview about their experience. Interview responses will be audio-recorded, transcribed verbatim, coded, and analyzed using qualitative data analysis software. All qualitative data analyses will be performed by the PI, Co-investigators, and/or authorized Research Assistants. Initial thematic analysis will incorporate codes suggested from the Health-ITUDEM.[71] Additional codes will be identified as they arise in the data. Rigor will be achieved through peer review of themes and by maintaining an audit trail of analytic memos.

IV. Protection of Human Subjects

A. Risks to Human Subjects

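### Secondary outcomes and mediators are compared by t-tests on change scores that leave out baseline and the other two features; adding them is a cheap, usually modest gain in precision.

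*Combined protocol and SAP*

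**What the plan says.** Section III gives the primary outcome, change in daily steps, a regression "adjusted for confounders (including presence/absence of other specialty features", their interactions and selected demographics, "and baseline daily steps". The same paragraph then turns to the other outcomes: "For secondary physical activity-related outcomes and proposed mediators, we will conduct multiple one-tailed t-tests", at a level of .10, "to further explore the potential viability of the specialty features". No covariate is named for these tests.

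That sentence does not say which score is tested. Section II.A.2 does: "Experimental outcomes will consist of pre-to-post change scores on PA-related and mediating variables".

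Nine variables are affected: sitting time, PASE, gait speed and the six mediators listed in Section III. With three features, that makes 27 comparisons. Table 1 shows that each is measured before and after the intervention, for example "Objective Sedentary Time | Dependent Variable | activPAL | Baseline and post".

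**The concern.** A change score uses baseline by subtraction, which fixes its slope at 1. Regression on baseline estimates the slope. In large samples the fixed slope is never more precise, and it is less precise whenever r differs from SDpre/SDpost. The t-test also leaves any effect of the other two randomised features in the error term.

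The stake is precision, not bias. Section II.A.2 warns against dropping features because a small sample failed to show an effect, and Section II.B says that the sample is about the largest that funding allows. When participants cannot be added, covariates already collected are the obvious remaining source of precision for the estimates that inform feature selection.

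**Working it through.** **Inputs from the documents.** 45 vs 45 per feature (II.A.2); 100 enrolled and 90 analysed (II.B); effect size 0.45, one-tailed .10, 80% power (III). The 0.45 is the planning value for the primary outcome and serves here only as an illustration.

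**Assumed, because the documents are silent.** r from 0.5 to 0.9; k = SDpost/SDpre of 1, 1.1 and 1.25. A k above 1 is plausible for activity measures because entry is restricted: candidates must "report <150 minutes of moderate-to-vigorous PA/week as per a single-item screener".

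**The plan's own figure.** A noncentral t with 88 df and noncentrality 0.45 × √(45/2) gives 80.0% power. The stated 80% reproduces.

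**Variance with and without the baseline covariate.** Set SDpre = 1.
- Change score: 1 + k² − 2rk
- Baseline-adjusted: k²(1 − r²)
- Saving: (1 − rk)², which is zero only at r = 1/k

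Example, k=1 and r=0.5: change variance 1 + 1 − 1 = 1; adjusted 1 − 0.25 = 0.75; ratio 0.750. Example, k=1.25 and r=0.8: change 1 + 1.5625 − 2 = 0.5625; adjusted 1.5625 × 0.36 = 0.5625; ratio 1.000.

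**Cost of the extra terms.** Simulation of the 2×2×2 design (100 randomised, 90 retained, 20,000 replicates per case) gave a mean variance inflation of 1.5%. Residual df fall from 88 to 85. So net ratio = ratio × 1.015, and net power uses effect 0.45/√(net ratio) with 85 df. The equivalent sample size under the t-test is 90/(net ratio).

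| r | k=1: ratio, net power, equivalent N | k=1.1: ratio, net power, equivalent N | k=1.25: ratio, net power, equivalent N |
|---|---|---|---|
| 0.5 | 0.750, 87.6%, 118 | 0.818, 85.3%, 108 | 0.893, 82.9%, 99 |
| 0.6 | 0.800, 85.9%, 111 | 0.870, 83.6%, 102 | 0.941, 81.4%, 94 |
| 0.7 | 0.850, 84.3%, 104 | 0.921, 82.0%, 96 | 0.981, 80.2%, 90 |
| 0.8 | 0.900, 82.7%, 99 | 0.968, 80.6%, 92 | 1.000, 79.6%, 89 |
| 0.9 | 0.950, 81.1%, 93 | 1.000, 79.6%, 89 | 0.950, 81.1%, 93 |

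The net ratio exceeds 1, so there is no gain, for r above 0.97 (k=1), about 0.84 to 0.95 (k=1.1) and about 0.71 to 0.86 (k=1.25). The largest loss is the cost alone, from 80.0% to 79.6%.

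**Interval width.** The 95% half-width in change-score SDs is t × √(2/45) × √(net ratio). The t-test gives 0.42. Adjusted, with k=1, it is 0.37 (r=0.5), 0.40 (r=0.8) and 0.41 (r=0.9). With k=1.25 it is 0.40 (r=0.5) and 0.42 (r=0.8).

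**Leaving out the other two features.** If each has effect d, the t-test error variance becomes 1 + 2(d/2)². For d=0.2 this is 1.020 and power is 79.4%. For d=0.45 it is 1.101 and power is 77.1%. Most of the gain therefore comes from baseline.

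**Simulation check, other features inert.** T-test vs adjusted power: 79.8% vs 87.6% (r=0.5, k=1); 80.0% vs 82.8% (r=0.8, k=1); 79.9% vs 79.6% (r=0.8, k=1.25). Type I error at r=0.5, k=1 was 9.9% for both.

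**The case against.** The strongest reply is that nothing here is wrong. The tests are valid and openly exploratory. Section II.A.2 plays down significance testing and "instead will incorporate the total array of relevant information (e.g., effect sizes, usage rates, satisfaction ratings"). Keeping the adjusted model for the primary outcome and using simple tests elsewhere is defensible in a pilot. The gain also depends on quantities that the documents do not give: at r=0.8 the net change is +2.7, +0.6 and −0.4 power points for k=1, 1.1 and 1.25. The plan promises no confidence intervals for these outcomes, and a half-width that moves from 0.42 to 0.40 may change no decision. Omitting the other features costs little, because the crossed design keeps them nearly orthogonal.

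All of this stands as a limit on size, and it is why the point is an improvement and not a defect. It does not favour the t-test. Over the range examined the possible gain is nearly 8 power points against a possible loss of about half a point. A plan that selects features on effect sizes benefits from tighter estimates even where p-values count for little.

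One further point affects only the illustration. Gait speed is measured only at in-person sessions (Sections II.C and IV.A.2), so 45 vs 45 may not hold for it. At an assumed 30 per group with equal SDs, power is 67% unadjusted and about 70% (r=0.8) to 76% (r=0.5) adjusted, so the direction is the same.

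**Conclusion.** The concern holds as a point of efficiency. The plan adjusts only the primary outcome, and no section adds baseline or feature covariates for the other nine variables. With equal SDs, adjustment is worth 1.1 to 7.6 power points (r=0.9 down to 0.5), or about 93 to 118 participants in place of 90. With a post SD 1.25 times baseline, the change runs from a loss of 0.4 point to a gain of 2.9 points. These figures rest on assumed r and k and on an effect size borrowed from the primary outcome. The primary analysis is unaffected. App usage and satisfaction are outside the point because they have no baseline value.

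**What to change.** Replace the t-tests for secondary physical activity outcomes and mediators with a linear regression of each change (or post) score on its own baseline value and the three feature indicators. Code the indicators −½/+½ so that each coefficient is the present-minus-absent difference. Once baseline is in the model, the feature estimate is the same for change and post scores. Report each adjusted difference with a confidence interval. This is the primary model without its interactions and demographics.

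The cost is one SAP sentence and a little analyst time. No new data are needed, and no participants are lost, because a change score already requires both measurements. The statistical price is about 1.5% in variance plus three degrees of freedom, which is not recovered where r is close to SDpre/SDpost.

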The specific aim of the clinical trial phase of this study is to **conduct a pilot test to examine key performance characteristics of the PA-tracking core app and its three specialty features.** This will include the MOST Screening Phase: theory-guided experimentation to identify viable components within a multifaceted preliminary intervention plan.[24] Using a factorial design as specified in MOST procedures, 100 underactive older people (i.e., those accumulating <150 minutes of at least moderate intensity activity/week)[8, 26] will be randomly assigned to one of eight conditions which reflect all possible combinations of presence vs. absence of the three respective specialty features, given usage of the core PA-tracking app. At the end of a four-month intervention period, for the core app as well as for each specialty feature we will examine changes from baseline in *objective PA, SA time, self-reported PA, and functional mobility.* We will also test the association between the app component features and theoretically postulated mediating constructs (*self-efficacy, self-regulation, outcome expectation, social support, aging self-perception, and views of aging*). In addition, we will document *usage rate and satisfaction* with the app.

II. Approach & Methods

A. Clinical Trial Design

This two-part study initially involves a two-week field test of the PA-tracking app suite followed by a focus group and then a four-month trial of the refined suite. This later segment is the focus of this clinical trial protocol description. A description of the app suite and details of the trial design are provided in the subsequent sections.

A.1. App Intervention

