Our biostatistician will secure and archive data, and will oversee all data analytic functions. Usage data for each participant will be obtained from storage within the app and downloaded manually at in-person assessment sessions. Data will be transferred to the biostatistician for analysis and storage on the USC secure network. activPAL data will be downloaded and cleaned. Using proprietary algorithms supplied by PAL Technologies, waking-hour wear periods will be identified for use in analysis.

Data analysis will be organized around the goal of providing multiple sources of information useful for future efforts to optimize the Moving Up app suite. We will calculate *descriptive statistics* at baseline and/or post-intervention for demographic, *app usage behavior* [proportion of days opening the app ≥ 1 time], *user satisfaction* [perceived app quality, physical activity-related (*objective physical activity* [primary outcome; daily steps], *sedentary activity time* [daily sitting time], *self-reported physical activity*, *functional mobility* [gait speed]), and mediational (i.e., *self-efficacy for physical activity*, *self-regulation for physical activity*, *family social support for physical activity*, *outcome expectation for physical activity*, *aging self-perceptions*, *views of aging*) outcome variables, both for the overall sample and by on/off status of each of three specialty features (i.e., Proof Positive, Coach Me, and On Your Feet).

Indicator variables will be created to code whether or not the participant had each of the specialty features installed on their phone as part of the intervention. Results regarding outcomes and hypothesized mediators will be calculated overall and by feature subgroup. The feature subgroups are not mutually exclusive since a participant can be randomized to receive 0, 1, 2, or all 3 of the features.

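### Table 1 assigns the six mediators to mediation testing, but the analyses planned in Section III address the separate links and do not amount to a mediation test (minor)

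*Combined protocol and SAP*

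**What the plan says.** Table 1 (Section II.C) lists a primary role for every variable. For all six mediators (views of aging, aging self-perceptions, and the self-regulation, self-efficacy, outcome expectation and social support scales) that role is "Tests of Mediation". The row for the first reads "Views of Aging | Tests of Mediation | Attitudes to Ageing Questionnaire [24 items". Each mediator is measured at baseline and post-intervention.

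Section III plans three things for them:

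- Summaries: "Results regarding outcomes and hypothesized mediators will be calculated overall and by feature subgroup".
- Feature comparisons: for secondary activity outcomes and "proposed mediators, we will conduct multiple one-tailed t-tests", at α = .10.
- Links to the primary outcome: "Correlation coefficients will be calculated to assess associations between the primary outcome (change in daily steps) and proposed mediators".

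The primary step-change model adjusts for the other features, their interactions, four demographic variables and baseline steps. No mediator is among its listed terms.

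Three other places bear on the point. The specific aim of the trial phase is to "test the association between the app component features and theoretically postulated mediating constructs". Section II.A.2 defines the scale: "Experimental outcomes will consist of pre-to-post change scores on PA-related and mediating variables". The same section says of component evaluation that "we will downplay the importance of (though still include) significance testing of PA outcomes".

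**The concern.** A mediation analysis needs three things: the effect of the feature on the mediator, the relation of the mediator to steps with the feature held fixed, and some way of combining the two. The t-tests supply the first. The correlation is the only analysis that relates mediator to steps, and it is not stated to hold the features fixed. Nothing combines the two: the plan has no indirect effect, no outcome model containing a mediator, and no joint test.

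The correlation has a specific weakness in this role. Change scores remove stable differences in level between people, but not the effect of the randomised features. A feature that raises both mediator and steps by separate routes produces a positive correlation even when the mediator has no effect on steps. A reader of Table 1 could take a significant t-test plus a positive correlation as evidence of mediation and carry that into the design of the later trial.

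**Working it through.** **The plan's own figure.** The documents give no figure for mediation. The related figure is 80% power for one feature's effect on steps (Section III: N = 90, effect size .45, one-tailed α = .10; Section II.A.2: 45 vs 45). Check: 0.45 × √(45/2) = 2.135; 2.135 − 1.282 = 0.853; Φ(0.853) = 0.803 (0.800 with the noncentral t). It reproduces, but covers only the feature effect on steps.

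**Set-up for the correlation.** From the documents: N = 90, 2×2×2 factorial, effect size 0.45, one-tailed .10. Assumed: unit SD of change within feature cell; k of the three features act, each moving mediator change and step change by the same d; no mediator-to-steps path.

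**Expected r.** A balanced on/off feature has variance 1/4, so each acting feature adds d²/4 to the covariance and to each variance:

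r = (k·d²/4) / (1 + k·d²/4)

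- d = 0.45: d²/4 = 0.0506. For k = 1, 2, 3, r = 0.0506/1.0506 = 0.048; 0.1013/1.1013 = 0.092; 0.1519/1.1519 = 0.132.
- d = 0.3: 0.022 for k = 1 and 0.063 for k = 3.
- d = 0.2: 0.010 for k = 1 and 0.029 for k = 3.

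**How often r would be significant, if it were tested.** By Fisher's z, the probability is 1 − Φ(1.282 − atanh(r)·√(N − 3)). At d = 0.45 and N = 90, atanh(r)·√87 is 0.450, 0.860 and 1.237, giving 20%, 34% and 48%.

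**Simulation** (20,000 trials per case). The adjusted model regresses step change on mediator change, the three features, all their interactions, four demographic terms, baseline steps and baseline mediator. The assumed correlation of baseline with change is −0.4.

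| d | acting features | mean r | r significant | adjusted coefficient significant | r > 0.3 |
|---|---|---|---|---|---|
| 0.45 | 1 | 0.048 | 20.1% | 9.7% | 0.7% |
| 0.45 | 2 | 0.094 | 34.8% | 10.2% | 2.1% |
| 0.45 | 3 | 0.133 | 49.2% | 9.6% | 5.0% |
| 0.3 | 1 | 0.021 | 13.8% | 9.7% | not tabulated |
| 0.3 | 3 | 0.064 | 24.7% | 9.6% | not tabulated |
| 0.2 | 1 | 0.009 | 11.5% | 9.7% | not tabulated |
| 0.2 | 3 | 0.030 | 15.7% | 9.6% | not tabulated |

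Setting the baseline-change correlation to 0 gives the same picture (one feature, 19.9% vs 9.7%; three, 49.4% vs 9.6%).

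**Reporting by feature subgroup.** Suppose the correlation is computed within the on or off group of one acting feature (n = 45). That feature's contribution vanishes and k − 1 remain, so r is 0, 0.048 or 0.092 and atanh(r)·√42 is 0, 0.313 or 0.598. The same formula gives 10%, 17% and 25%, and simulation agrees. If the subgroup is defined by a feature that does not act, one acting feature elsewhere still contributes in full: r = 0.048 with n = 45, again 17%.

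**Limit of adjustment.** Add an unmeasured shared cause, with a correlation of 0.3 between the residuals of mediator change and step change after baseline. With one acting feature at 0.45, r is significant in 93.6% of trials and the adjusted coefficient in 92.2%. Both are wrong, because the mediator still has no effect on steps.

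**The case against.** The strongest case on the other side is that this is a loose label and nothing more. Table 1 is a measurement overview and names no specific test. The aim promises only feature-mediator association, which the t-tests deliver. Section III claims only that the correlations describe association, and Section II.A.1 offers its pathway diagram as a heuristic. This largely stands: it fixes the size of the point as small and is why renaming the role is part of the remedy. It does not reconcile Table 1 with Section III, which are both current text.

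A reader might infer that the plan will declare false mediation in up to half of trials. The documents do not support that. Section III states no significance test for the correlations, the 49% needs all three features acting at 0.45 SD on both variables, and the expected bias in r is at most about 0.13 in the cases examined.

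The subgroup sentence in Section III may already help, but only in part: it does not expressly name the correlations, and each subgroup still mixes the other two features.

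It can also be said that 18 unpowered indirect effects in a pilot would invite more overclaiming than a plain correlation. That is fair, and it is why the indirect effect is only optional here.

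**Conclusion.** The mismatch holds and is minor. Followed exactly, the plan yields evidence on the separate links but no mediation test, and its one mediator-outcome analysis can absorb feature effects.

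The distortion is small as a description: mean r about 0.05 to 0.13 at d = 0.45 and 0.01 to 0.03 at d = 0.2. It would matter more if r were tested at one-tailed .10: about 20% to 49% significant at d = 0.45 overall, or about 10% to 25% within subgroups of an acting feature, against about 10% with adjustment. These figures assume equal effects on both variables, no true mediator-to-steps path and no shared cause.

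A reader might also infer that the trial fails its aim or that its main result is at risk. Neither follows. The aim asks only for feature-mediator association. The inputs to component selection that Section II.A.2 gives as examples are effect sizes, usage and satisfaction, not mediation. The primary analysis and sample size are unaffected.

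**What to change.** 1. For each mediator, estimate its association with steps as the coefficient of mediator change in the Section III step-change model: same features, interactions, demographics and baseline steps, plus baseline mediator.
2. Keep the raw correlation as descriptive, and say whether it is computed overall, by feature subgroup, or both.
3. Change the Table 1 role to exploratory mediator analyses, to match the aim.
4. State that adjustment does not remove unmeasured common causes, and that with baseline and post measurements only, temporal order is not established.

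An indirect effect with a bootstrap interval is optional. If reported, label it exploratory, unpowered and without a multiplicity claim. In simulation with a feature-to-mediator effect of 0.45 and an assumed mediator-to-steps effect of 0.3 (indirect effect 0.45 × 0.3 = 0.135 SD), the 80% interval is about ±0.11 SD and lies above zero in 73% of trials. With no mediator-to-steps effect but a shared cause (residual correlation 0.3), it lies above zero in 75%, so such an interval could not be read as evidence of mediation by itself. Six mediators by three features gives 18 combinations, assuming one score per construct. With neither path present, about 1.8 to 1.9 of the 18 intervals would be expected above zero under that shared cause; the figure falls to 0.2 (18 × 0.011) only if there is no shared cause.

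Cost: a little analyst time and a few lines of text. All the measures are already planned at baseline and post, so nothing new is collected.
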